Fixed-Dose Netupitant and Palonosetron for Chronic Nausea and Vomiting in Cancer Patients

Principal Investigator: [name]
Co-Principal Investigator: [name]
Collaborators: [name], [name], [name], [name]
[name], [name], [name], [name], [name]
[name]
Biostatistics Collaborators: [name], [name]

Table of Contents

A. Study Objectives	2
B. Background	2
C. Pharmaceutical Information	5
D. Experimental Approach	7
E. Patient Withdrawal Criteria	13
F. Investigator Communications with Helsinn	
G. Serious Adverse Events Reporting	16
H. Statistical Considerations	17
I. Data Confidentiality Procedures	
J. References	

A. Study Objectives

Primary objective:

To estimate the efficacy (i.e. change in nausea numeric rating scale [NRS] from baseline between day 5-15) of fixed dose netupitant and palonosetron (NEPA) for chronic nausea in cancer patients.

Secondary objective:

- 1. To assess the secondary outcomes (e.g. proportion of patients who achieved their personalized nausea goal, antiemetic use, nausea episodes duration/frequency) for NEPA vs. placebo.
- 2. To assess the adverse effects associated with NEPA and placebo.

B. Background

B.1. Significance of Chronic Nausea in Cancer Patients. Nausea is defined as "an unpleasant sensory and emotional experience, which may be described in terms of a sick feeling with or without a sense of impending vomiting/retching - often associated with a perception of epigastric or upper abdominal unpleasantness or awareness".¹ Chronic nausea is defined as nausea of 1 month or greater.^{2,3} In one systematic review of 39 studies consisting of 24263 patients with incurable cancer, nausea occurred in 31% (95% confidence interval [CI] 27-35%) of patients, and vomiting in 20% (95% CI 17-22%).⁴ In another systematic review of far advanced cancer patients, the prevalence of nausea was estimated to be 6-68%.⁵ Rhondali et al. reported that among 444 cancer patients seen at the supportive care clinic at MD Anderson Cancer Center, 112 patients had moderate/severe chronic nausea of >=4/10 in intensity.⁶ 68/112 (61%) patients had a response (defined as 30% improvement from baseline) to the multimodal therapies offered by the palliative care team (e.g. metoclopramide, ondansetron, other anti-emetics, constipation management, counseling) at the followup visit 2 weeks later.

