B.3. The Current Management of Chronic Nausea. A systematic review highlighted the paucity of robust studies to inform the management of nausea and/or vomiting unrelated to chemotherapy or radiation. Among the 93 studies on this topic, 14 were RCTs. Table 1 includes the key randomized trials on chronic nausea to date. Metoclopramide had modest evidence based on randomized controlled trials and prospective cohort studies. There were also some evidence to support the use of octreotide, dexamethasone and hyoscine butylbromide for nausea related to bowel obstruction. The authors concluded that "there are discrepancies between antiemetic studies and published antiemetic guidelines, which are largely based on expert opinion. Antiemetic recommendations have moderate to weak evidence at best. Prospective randomized trials of single antiemetics are needed to properly establish evidence-based guidelines."¹³

Study	Patients	Design	Interventions	Outcome
Bruera et al. Cancer 1994 ²²	N=34 Advanced cancer Nausea >1month	DB-RCT crossover	Metoclopramide CR 40 mg q12h vs. metoclopramide IR 20 mg q6h x3d then crossover	Nausea VAS on day 3:15 vs. 8 P=0.047
Bruera et al. JPSM 2000 ²	N=26 Advanced cancer Nausea >1month	DB-RCT crossover	Metoclopramide CR 40 mg q12h vs. placebo x4d then crossover	Nausea VAS on day 4:17 vs. 12
Bruera et al. JPSM 2004 ²³	N=51 Nausea >2w despite 48h of metoclopramide	DB-RCT	Metoclopramide 60 mg daily + either dexamethasone 20 mg daily or placebo x7d	Nausea NRS on day 3: 4.5 vs. 2.9 (P=0.16), day 8: 5.9 vs. 5.9 (P=0.85)
Corli et al JPSM 1995 ²⁴	N=30 Advanced cancer	DB-RCT, crossover	Levosulpride 75mg daily vs. metoclopramide 30 mg daily x7d	Hours with nausea 1.8 vs. 2.01, nausea VAS 0.75 vs. 1.42, (P=0.0004)
Hardy et al. SCC 2002 ²⁵	N=92 Opioid induced nausea	DB-RCT	Ondansetron 24 mg daily, metoclopramide 10 mg TID vs. placebo x1d	Complete control of nausea: 17%, 36%, 23% (P=NS) Early termination
Brown et al. AJHPC 1992 ²⁶	N=6 Hospice	OL-RCT	Acupressure wrist band, placebo wrist band, no wrist band	Not effective
Mystakidou et al. Oncologist 1997 ²⁷	N=120 Far advanced cancer despite metoclopramide	OL-RCT	Metoclopramide + dexamethasone, Metoclopramide + tropisetron, vs.	Total control of nausea d15: 18%, 74%, 87% Total control of vomiting 24%, 84%, 92%

 Table 1. Randomized Controlled Trials on Antiemetics for Chronic Nausea and

 Vomiting

			Metoclopramide + dexamethasone + tropisetron x15d	

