- Additionally, any serious adverse events that occur after the 30 day time period that are related to the study treatment must be reported to the IND Office. This may include the development of a secondary malignancy.

Reporting to FDA:

• Serious adverse events will be forwarded to FDA by the IND Sponsor (Safety Project Manager IND Office) according to 21 CFR 312.32.

It is the responsibility of the PI and the research team to ensure serious adverse events are reported according to the Code of Federal Regulations, Good Clinical Practices, the protocol guidelines, the sponsor's guidelines, and Institutional Review Board policy.

H. Statistical Considerations

The primary objective of this phase II study is to estimate the effect of NEPA on the nausea numeric rating scale (i.e. change between day 5 and day 15). The target accrual is 30 evaluable patients who complete the study with a randomization ratio of 2:1 (NEPA vs Placebo), but accrual will range from 41-50, given an attrition rate of 30-40%. With 20 patients in the NEPA arm, we would have a 92% power to detect a difference of 2 points with a standard deviation of 2.5 (effect size of 0.8) using two-sided paired t-test with a significance level of 0.05.

Descriptive statistics, including mean, standard deviation, 95% confidence intervals, median, range, frequency and percentage will be summarized for all variables of interest such as patients' demographics, clinical characteristics, personalized nausea goal, NRS and adverse effects, whichever appropriate.

We will focus on estimating the magnitude of change in NRS between day 5 and day 15. We will use a mixed model to examine the change in nausea overtime in both the NEPA arm and placebo arm.

We will estimate the proportion (with 95% confidence interval) of patients who achieve their personalized nausea goal for NEPA and placebo as a secondary outcome. Adverse effects associated with NEPA and placebo will be collected and frequency will be summarized.

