A comparison between NEPA and placebo is not the objective of this study. However, Chi-squared test or Fisher's exact test, whichever the most appropriate, will be used to test for association between categorical variables, such as CTCAE adverse effects, global assessment, and blinding. Wilcoxon rank sum test or Kruskal-Wallis test will be used to test for difference of continuous variables, such as ESAS and FLIE. General linear model may be considered to examine the effect of potential important factors on NRS.

A Response/Toxicity Summary will be submitted to the IND Office Medical Monitor, after the first ten evaluable patients complete study treatment, and every 10 evaluable patients thereafter.

I. Data Confidentiality Procedures

This study will be monitored by the MD Anderson IND Office and a protocol-specific monitoring plan will be followed.

All records identifying the subject will be kept confidential and, to the extent permitted by the applicable laws and/or regulations, will not be made publicly available.

During the study, trained research staff will be performing study assessments and monitoring the patient carefully throughout the study period. Regulatory monitoring will be provided by the principal investigator and the IND office. Patient confidentiality will be maintained by use of unique study numbers, secure storage of clinical data, and anonymous reporting.

Collection of identifiers: We will collect and securely store patients' identifiers (including name and medical record number). Each patient will be assigned a study number that will be the only identifier to figure in the analytical file and personal data will not be disclosed in any form. The key linking these numbers will be retained in a securely locked file by the investigator.

Data Storage: Protection of electronic and paper records will be maintained to the best of our ability. All electronic records will be stored on password-protected institution computers behind the institution firewall. Any paper records will be classified and stored in locked files inside a locked office.

Training of personnel: Only MDACC personnel trained in maintaining confidentiality, the principal investigators, co-investigators, and the research team will have access to study records.

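### Sections A and H treat the day 5 to day 15 NRS change as NEPA's effect, and no NEPA-minus-placebo difference with a confidence interval is specified for NRS

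*Combined protocol and SAP*

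**What the plan says.** Section A gives the primary objective as "To estimate the efficacy (i.e. change in nausea numeric rating scale [NRS] from baseline between day 5-15) of fixed dose netupitant and palonosetron (NEPA"). Section H repeats it: the primary objective "is to estimate the effect of NEPA on the nausea numeric rating scale (i.e. change between day 5 and day 15"). The power statement takes 20 patients in the NEPA arm, a 2-point difference and an SD of 2.5, and obtains 92% power "using two-sided paired t-test with a significance level of 0.05". Placebo patients do not enter that calculation.

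For the NRS itself, Section H plans three things:

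- descriptive statistics, including 95% confidence intervals;
- a longitudinal model: "We will use a mixed model to examine the change in nausea overtime in both the NEPA arm and placebo arm";
- an optional model: "General linear model may be considered to examine the effect of potential important factors on NRS".

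It then states: "A comparison between NEPA and placebo is not the objective of this study". It nevertheless goes on to name chi-squared or Fisher tests for categorical variables, and rank tests for continuous variables, with ESAS and FLIE as examples.

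The design is comparative. D.1 describes a double-blind, parallel-group, placebo-controlled randomised trial. Its main goal is an effect size for each arm, to inform a larger confirmatory randomised trial. D.4 randomises 2:1, stratified by pre-randomisation NRS (4-6 or 7-10). The first secondary objective is worded as NEPA versus placebo.

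**The concern.** The words effect and efficacy are attached to a change within one arm. Such a change mixes whatever NEPA does with whatever would have happened without it. Four sources of improvement without the drug are visible in the design:

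- ordinary fluctuation of a subjective symptom;
- regression to the mean, because D.4 requires an NRS of at least 4 shortly before the day 5 to day 15 change begins, and patients below 4 are watched to day 7 and randomised if nausea rises again;
- as-needed metoclopramide (D.7, D.8);
- placebo response that persists after the run-in.

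The blinded placebo arm can separate these from the drug, but only through the difference between arms. That difference and its uncertainty are also what the larger trial needs. If it is not prespecified, the adjustment used, and whether the difference is reported as a result at all, can be settled after the data are seen.

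**Working it through.** **Inputs.** From Section H: 30 evaluable patients at 2:1, so 20 NEPA and 10 placebo; difference 2 points; SD 2.5; two-sided 5% level. From D.10: minimal clinically important difference 1 point. Assumption: the SD of change is also 2.5 on placebo, since the protocol gives no separate value.

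**1. The plan's own figure.** Paired t-test, n = 20. Noncentrality = (2/2.5) × √20 = 0.8 × 4.472 = 3.578, with 19 df. Noncentral t power = 92.4%. The stated 92% is reproduced as power for a within-arm change.

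**2. The same test when NEPA adds nothing.** Suppose both arms improve by the same amount m, so the true NEPA-minus-placebo difference is zero. The paired test in the NEPA arm has noncentrality (m/2.5) × √20. The values of m are assumptions.

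| Shared improvement m | Noncentrality | Probability that the NEPA-arm test is significant |
|---|---|---|
| 1 point | 1.79 | 40% |
| 1.5 points | 2.68 | 72% |
| 2 points | 3.58 | 92% |

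**3. Precision within arms and between arms (95% half-widths).**

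- NEPA alone: t(19) × 2.5/√20 = 2.093 × 0.559 = ±1.17.
- Placebo alone: t(9) × 2.5/√10 = 2.262 × 0.791 = ±1.79.
- Difference, unadjusted: SE = 2.5 × √(1/20 + 1/10) = 0.968; t(28) × SE = 2.048 × 0.968 = ±1.98. At an SD of 2.0 this is ±1.59, and at 3.0 it is ±2.38.

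**4. Power for the difference.** Two-sample t, 28 df, noncentrality 2/0.968 = 2.07: 51% for 2 points. For 1 point it is 17%. Power of 80% is reached at 2.81 points.

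**5. Adjusting for pre-randomisation NRS (27 df, SD of change held at 2.5).**

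- If the day-5 and day-15 variances are equal, the residual SD is 2.5 × √((1 + ρ)/2). For assumed correlations of 0.3, 0.5 and 0.7 the half-widths are 1.60, 1.72 and 1.83, and power for 2 points is 70%, 63% and 58%.
- Entry at NRS of at least 4 narrows the baseline spread. With an assumed baseline SD s0 of 1.25 to 2.0, solve s1² + s0² − 2ρ·s0·s1 = 6.25 for the day-15 SD s1; the residual SD is s1 × √(1 − ρ²). Over the same correlations the half-width runs from 1.68 to 1.99 and power for 2 points from 51% to 65%. At s0 = 1.5 and ρ = 0.5 the half-width is 1.99, so adjustment gains nothing.

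**The case against.** The strongest reply is that the protocol uses effect for the response within an arm. D.1 speaks of an effect size for both NEPA and placebo, so Section H's wording could be a defined term and not a claim of net benefit. The study is openly a 30-patient proof of concept with no decision rule. Its power statement says plainly that it concerns the NEPA arm and a paired test. An interval of about ±2.0 points against a 1-point minimal important difference is itself a reason not to make the comparison the objective. Much of this stands: it is why the study should remain an estimation study. It does not make a single-arm change an estimate of efficacy, and D.1's purpose of planning a randomised trial calls for the difference.

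Several stronger readings are tempting and should not be drawn:

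- *The placebo arm is ignored, or NRS has no confidence intervals.* Neither is so. The mixed model covers both arms and descriptive 95% CIs are planned for NRS. If they are given by arm, a crude difference can be worked out by hand. What is missing is a specified difference with its own interval.
- *No between-arm test could touch nausea.* The rank tests are introduced by examples, so they might extend to NRS, and ESAS includes a nausea item. They are tests, however, and yield no estimated difference with a CI.
- *The background shows how much placebo patients will improve.* It does not. In B.1, "68/112 (61%) patients had a response (defined as 30% improvement from baseline) to the multimodal therapies offered by the palliative care team", but that cohort was actively treated and had no placebo run-in. The Table 1 entry "Complete control of nausea: 17%, 36%, 23% (P=NS") comes from a one-day study of opioid-induced nausea that ended early. Another Table 1 trial reports a day-8 NRS of 5.9 in both arms, with no baseline shown. These are context only.

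The run-in removes some early placebo responders and so reduces the problem. It does not remove later response or regression to the mean.

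**Conclusion.** The concern holds in this form: Sections A and H attach efficacy and effect to an uncontrolled change, and no NEPA-minus-placebo NRS difference, arm-by-time contrast or CI for it is specified, although a blinded, NRS-stratified placebo arm is available. It should be fixed. It affects how the primary result will be read and how the next trial is sized; it does not invalidate the study.

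A reader might infer that the 92% power is wrong. It is not: it is right for a within-arm change and says nothing about NEPA against placebo, for which power at 2 points is 51% unadjusted. The between-arm figures assume an SD of 2.5 on placebo; the 40% to 92% range rests on assumed shared improvements of 1 to 2 points; the adjusted precision depends on assumed correlations and baseline spread.

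**What to change.** Keep the study as estimation and amend the wording.

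1. **Section H, estimate of effect.** Name the NEPA-minus-placebo difference in day 5 to day 15 NRS change, with 95% CI, as the estimate of NEPA's effect, adjusted for the pre-randomisation NRS already collected. Either ANCOVA of day-15 NRS or the arm contrast at day 15 from the planned mixed model would serve; choose one in advance.
2. **Section H, labels.** Describe the single-arm estimates and the 92% power as within-arm change.
3. **Section H, disclaimer.** Replace the sentence saying that the comparison is not the objective with one saying that the study is not powered for it. State the expected precision: about ±2.0 points unadjusted, 1.6 to 2.0 adjusted, and 51% unadjusted power for 2 points, at an SD of 2.5 in both arms.
4. **Section A.** Align the primary objective.

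As a secondary clarification, D.10 could name the baseline score, because randomisation may fall on any day from 3 to 7 and both 24-hour and 5-day averages are collected.

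The cost is a protocol amendment, with no extra patients or data. The headline interval widens from about ±1.2 to about ±2.0 points unadjusted, and adjustment may recover nothing.

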- Proportion of patients with complete response—defined as no significant nausea (average NRS≤2), no rescue medication for nausea/vomiting and no emesis. A vomiting episode is defined as a single vomiting episode (defined as expulsion of stomach contents), a single retching (defined as an effort to vomit without expulsion of stomach contents) or any retching combined with vomiting.^{27-29,31}
- Global symptom evaluation we will assess impression of change by asking them about their nausea and vomiting (worse, about the same, or better; If better, how

much better? Hardly any better, a little better, somewhat better, moderately better, a good deal better, a great deal better, a very great deal better; If worse, how much worse? Hardly any worse, a little worse, somewhat worse, moderately worse, a good deal worse, a great deal worse, a very great deal worse) comparing between the level of nausea and vomiting days 1-5 vs. days 6-15. Study satisfaction will be assessed with the following questions, "Was it worthwhile for you to participate in this research study?", "If you had to do it over, would you participate in this research study?", "Did your quality of life get better by participating in this research study?", "Did your quality of life get worse by participating in this research study?" Blinding will be assessed by asking patients and study staff which group assignment they believe they received: "NEPA", "placebo", or "do not know".

- Personalized Nausea Goal—we will assess personalized nausea goal by asking "At what level of intensity would you feel comfortable? 0-10 where 0=no nausea and 10=worst possible". Personalized nausea response is defined as nausea NRS ≤ personalized nausea goal. To assess stability of personalized nausea goal, we will be asking participants to provide this on day 15±2 as well.

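### The global impression of change is an ordered 15-grade scale, but section H assigns it to chi-squared or Fisher's test, which ignores order and direction

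*Combined protocol and SAP*

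**What the plan says.** Section D.10, under the global symptom evaluation, and footnote 8 of Table 4 describe the item in two steps. The first gives the direction, by "asking them about their nausea and vomiting (worse, about the same, or better; If better, how" and so on. The second gives the size. Those who improved choose among "Hardly any better, a little better, somewhat better, moderately better, a good deal better, a great deal better, a very great deal better". Those who worsened choose among "Hardly any worse, a little worse, somewhat worse, moderately worse, a good deal worse, a great deal worse, a very great deal worse". Table 4 schedules the item once, at day 15±2.

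Section H names two families of test for comparing the arms. The first is "Chi-squared test or Fisher's exact test, whichever the most appropriate", which "will be used to test for association between categorical variables, such as CTCAE adverse effects, global assessment, and blinding". The second is for scores: "Wilcoxon rank sum test or Kruskal-Wallis test will be used to test for difference of continuous variables, such as ESAS and FLIE". The global assessment is in the first list and not in the second. The text supplies no numeric score, trend test, ordinal model or rule for grouping the grades. The form itself (Appendix F) is not part of the text available for this review.

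**The concern.** Of the three examples in the first list, the blinding guess (NEPA, placebo, do not know) has no order, so an unordered test suits it. The global assessment has a clear order and a sign. An unordered test treats the two ends of the scale like any other pair of labels, and asks only whether the arms differ in some way, not whether NEPA patients report more improvement.

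A real shift towards better is therefore harder to detect than it need be. The study is meant to inform a larger trial, and the global item is the patients' direct rating of change, so a weak test wastes part of what is collected. Section H also leaves open whether 15 or 3 categories enter the table, so that choice could be made after the data are seen.

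**Working it through.** **Inputs from the documents**

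- Levels: 7 worse + 1 same + 7 better = 15 (section D.10).
- Sample: "The target accrual is 30 evaluable patients who complete the study with a randomization ratio of 2:1 (NEPA vs Placebo"), that is 30 × 2/3 = 20 and 30 × 1/3 = 10 (section H).
- Significance level 0.05, two-sided. Section H states this for the nausea rating only; it is assumed here for the global item.

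**The plan's own figure.** Section H says: "With 20 patients in the NEPA arm, we would have a 92% power to detect a difference of 2 points". With SD 2.5 the effect size is 2/2.5 = 0.8. The paired t-test has 19 degrees of freedom and noncentrality 0.8 × √20 = 3.58, which gives power 0.924. The stated 92% reproduces. It concerns the primary nausea rating within the NEPA arm; no power is stated for the global item.

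**Cell counts.** Spread evenly over 15 grades, the mean expected count is 20/15 = 1.33 per NEPA cell and 10/15 = 0.67 per placebo cell. The usual chi-squared approximation is unreliable at such counts, so Fisher's test or an exact chi-squared would be needed. That deals with the sparse cells but not with the order.

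**Order is ignored.** An illustrative table (not trial data), from -7 to +7:

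- NEPA: 1, 0, 1, 0, 1, 1, 2, 2, 3, 3, 2, 2, 1, 1, 0 (total 20)
- Placebo: 1, 1, 1, 1, 2, 1, 1, 1, 1, 0, 0, 0, 0, 0, 0 (total 10)

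| Order of grades | Chi-squared (13 df) | p | Wilcoxon p |
|---|---|---|---|
| True | 10.875 | 0.62 | 0.004 |
| Reversed | 10.875 | 0.62 | 0.004 |
| Scrambled | 10.875 | 0.62 | 0.55 |

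The top grade is empty in both arms, so 14 columns leave 13 df. Chi-squared is the same in every order, whereas the Wilcoxon result depends on the order being right. Collapsed to worse/same/better, the table is 6/2/12 against 8/1/1, with chi-squared 7.42 on 2 df and p = 0.025. The grouping rule alone thus moves the unordered result from 0.62 to 0.025.

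**Power.** A normal response was cut into the 15 grades, with 20 against 10 patients and 2,000 simulated trials per setting. Assumptions: two sets of cut-points, placebo centred at 0 or at 0.5 SD towards better, and a shift of 0.8 SD (borrowed from the effect size for the nausea rating) or 1.2 SD. Ranges are over these settings.

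| Test | 0.8 SD | 1.2 SD |
|---|---|---|
| Fisher or exact chi-squared, 15 grades | 0.11-0.25 | 0.29-0.59 |
| Ordinary chi-squared, 15 grades | 0.05-0.13 | 0.17-0.37 |
| Fisher or exact chi-squared, 3 levels | 0.31-0.37 | 0.54-0.66 |
| Wilcoxon, 15 grades | 0.46-0.48 | 0.81-0.82 |

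A second model used normal scores with SD 3 grades, rounded and limited to -7 to +7. In 2,500 runs it gave 14%, 33% and 46% at 0.8 SD (15 grades unordered, 3 levels, Wilcoxon) and about 24%, 48% and 68% at 1.0 SD.

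With no effect, the Wilcoxon test and the exact tests on 15 grades reject about 4-5% of the time; ordinary chi-squared on 15 grades rejects about 2%.

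**Relative loss at 0.8 SD.** For 15 grades, 0.25/0.46 = 0.54 and 0.11/0.48 = 0.23, so about half to three quarters of the rank test's power is lost. For 3 levels, 0.31/0.46 = 0.67 and 0.37/0.48 = 0.77, so about a quarter to a third is lost.

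**The case against.** The strongest reply is that little depends on this test. Section H says, just before naming these tests, that comparing NEPA with placebo is not the purpose of the study; its focus is the size of change in the nausea rating. This stands, and it limits the weight of the point. It does not remove it: section H goes on to commit to the tests, and the first secondary objective in section A sets NEPA against placebo on the secondary outcomes. A planned test should suit its scale.

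A second reply is that the first step of the item has three answers, so a three-category table may be what is meant. That is a fair reading, but the documents do not say it. Under it, order is still ignored and the 14 grades of size go unused.

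A third reply is that section H already promises medians, ranges, frequencies and percentages for all variables of interest, which would show the direction whichever test is used. This is largely right for description, though a median needs a score and none is defined.

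Some stronger readings are tempting but not supported:

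- A reader might infer that the plan throws away most of the item's information. At a moderate shift that holds only if all 15 grades enter the table, and section H does not say so.
- A reader might take the global item as the only patient-based guide to whether change mattered. Section D.10 also has the personalized nausea goal and a minimal important difference of 1 point on the nausea rating.
- A reader might fear false positive results. The exact tests keep close to the 5% level.
- A reader might expect the Wilcoxon test to make this comparison well powered. At 0.8 SD it still misses the shift slightly more than half the time; ten placebo patients are the main limit.

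**Conclusion.** The point holds as a mismatch between scale and test: section D.10 defines an ordered, signed outcome, section H gives it an unordered test, and nothing in the available text restores the order. The rank test was the more powerful choice in every setting tried with a true shift. How much is lost depends on the unstated choice between 15 and 3 categories. It also depends on the assumed shift, spread and cut-points, so the ranking of the tests is firmer than any single percentage. The consequence is modest and confined to one secondary outcome; the primary analysis, its 92% power and the sample size are untouched.

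**What to change.** In section H, take the global assessment out of the chi-squared/Fisher list and add it to the Wilcoxon rank-sum list with ESAS and FLIE. State the score: -7 for the worst grade, 0 for no change, +7 for the best. Report the median and the full distribution by arm; an effect estimate with a 95% confidence interval would suit the study's aim of estimation. If a worse/same/better summary is wanted, define it in advance and label it descriptive. Keep chi-squared or Fisher's test for the blinding guess.

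The cost is a sentence or two in section H. No new data, visits, patient burden or statistical procedure are needed.

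### Adverse effects: the only planned between-arm result is a chi-squared or Fisher test, with no interval for the arm difference, and at 20 vs 10 power is low for true excesses below about 40 to 50 points

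*Combined protocol and SAP*

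**What the plan says.** Section A makes safety the second secondary objective: "To assess the adverse effects associated with NEPA and placebo".

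Section H (Statistical Considerations) treats adverse effects in three places:

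- **Description.** It promises that descriptive statistics including "95% confidence intervals, median, range, frequency and percentage will be summarized for all variables of interest", and the list of those variables ends with "personalized nausea goal, NRS and adverse effects, whichever appropriate".
- **Frequencies.** "Adverse effects associated with NEPA and placebo will be collected and frequency will be summarized".
- **Testing.** After stating that "A comparison between NEPA and placebo is not the objective of this study", it nevertheless plans tests. The choice between chi-squared and Fisher is left to which suits the data better, and one of the two "will be used to test for association between categorical variables, such as CTCAE adverse effects, global assessment, and blinding".

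No risk difference, risk ratio or other between-arm measure with an interval is named for adverse effects. No significance level, power or analysis set is given for these tests. On size, section H says: "The target accrual is 30 evaluable patients who complete the study with a randomization ratio of 2:1 (NEPA vs Placebo". That is 20 on NEPA and 10 on placebo.

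**The concern.** The study is presented as proof of concept, meant to supply effect sizes for a larger trial (section D.1), and section H frames its main task as estimation. For adverse effects, however, the one result that sets the arms against each other is a significance test. With so few patients, a non-significant p-value is the likely outcome even when NEPA truly causes a material excess. The p-value does not tell the reader how large an excess remains possible. A planner of the next trial who wants to know how much extra constipation or headache the repeat-dose regimen might cause would learn little from it. An interval for the difference answers that question directly.

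**Working it through.** **The plan's own figure.** Section H states one power: 92% for a paired t-test within the NEPA arm (n = 20, difference 2, SD 2.5, two-sided 0.05). With noncentrality 0.8 × √20 = 3.58 and 19 degrees of freedom, the noncentral t gives 92.4%, so it reproduces. It concerns nausea scores within one arm. There is no corresponding figure for adverse effects.

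**Inputs.** From section H: 20 vs 10. Assumed, because the documents give none: a two-sided 0.05 level for the adverse-effect tests, and the true event rates, shown as a range. The only NEPA-related rates given (section D.7, chemotherapy setting) are constipation 3.6% and headache 1%.

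**Step 1: what Fisher's test flags.** With m events in total, the probability of k placebo events is C(20, m−k) × C(10, k) / C(30, m). The two-sided p-value adds all tables no more probable than the one observed.

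- 8/20 vs 0/10: 0.02152 + 0.00682 + 0.00041 + 0.00001 = 0.029, flagged.
- 7/20 vs 0/10: 0.03808 + 0.02352 + 0.00206 + 0.00006 = 0.064, not flagged, although the observed excess is 35 points.
- Against 1/10, the threshold is 10/20 (p = 0.049); 9/20 gives p = 0.10.

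The uncorrected chi-squared test gives p = 0.033 for 7/20 vs 0/10. The expected placebo count there is only 7 × 10/30 = 2.3, so Fisher's test is the appropriate choice.

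**Step 2: power.** Sum the binomial probabilities of all tables with p < 0.05. With a true placebo rate of 0%, this is P(X ≥ 8) for X ~ Bin(20, NEPA rate).

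| True NEPA rate | Placebo 0% | Placebo 10% |
|---|---|---|
| 20% | 3% | 1% |
| 30% | 23% | 10% |
| 40% | 58% | 30% |
| 50% | 87% | 54% |

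Power of 80% needs a true NEPA rate of about 47%, 55% or 65% when the placebo rate is 0%, 5% or 10%. At 3.6% vs 0%, power is essentially zero.

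**Step 3: a larger denominator.** Section H expects accrual of 41 to 50. As an upper bound, suppose all were randomised 2:1 and analysed.

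- Threshold against no placebo events: 8/28 (29%) vs 0/14, or 8/33 (24%) vs 0/17.
- Power at 30% vs 10%: 23% (28 vs 14) to 28% (33 vs 17). The first split has 42 patients; 27 vs 14, exactly 41, gives 20%.
- Power at 30% vs 0%: 64% to 82% for the same two splits, so against a zero placebo rate the larger set helps considerably.

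**Step 4: what the interval shows.** Newcombe's limits use the Wilson limits (l, u) of each arm:

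- lower = d − √[(p₁ − l₁)² + (u₂ − p₂)²]
- upper = d + √[(u₁ − p₁)² + (p₂ − l₂)²]

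For 6/20 vs 1/10, the Wilson limits are 14.5% to 51.9% and 1.8% to 40.4%. With d = 20 points, the interval is −14 to +43 points, where Fisher's test says only p = 0.37. For 4/20 vs 0/10, the difference is +20 points (−10 to +42), p = 0.27. With no events in either arm, the interval for the difference is −28 to +16 points, and the exact upper limit for 0/20 is 1 − 0.025^(1/20) = 16.8%.

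**The case against.** **Estimation is already planned.** Section H lists adverse effects among the variables to be described, with confidence intervals among the statistics. This stands: a reader might infer that safety will be reported by p-values alone, and the text does not support that. What is missing is an interval for the difference.

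**The tests are not blind to large effects.** A reader might also infer that at 20 vs 10 no excess, however large, can be flagged. The figures say otherwise: 8/20 vs 0/10 is significant, and power is 87% at 50% vs 0%.

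**A comparison is disclaimed.** Since section H says that comparing the arms is not the objective, leaving out a risk difference can be called consistent. This carries some weight, but the plan then tests adverse effects anyway. If a between-arm result is to be given, an estimate with its uncertainty fits the stated aim better than a test does.

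**Oversight does not rest on these tests.** Serious adverse event reporting (section G), the toxicity summary every ten evaluable patients (section H) and the monitoring board (section D.12) operate independently of them. This stands, and it limits the point to the final report. Nor do the documents say that a non-significant result would be read as absence of harm; that is a risk of interpretation.

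**The denominator may exceed 30.** The target counts completers, withdrawals are replaced (section E), and no safety set is defined. This also stands. Step 3 shows that it helps clearly when the placebo rate is zero and much less when it is 10%.

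**Conclusion.** The point holds in a limited form and is a minor improvement. The plan's only between-arm result for adverse effects is a test that, at 20 vs 10, has at most 23% power in the scenarios shown with a true NEPA rate of 20% to 30%, and reaches 58% to 87% only at 40% to 50% vs 0%. No interval for the arm difference accompanies it. This rests on a two-sided 0.05 level, on assumed event rates, and on the completer target as the denominator. With the whole accrual analysed, power at 30% vs 10% stays below 30%, while at 30% vs 0% it becomes moderate to good. The documents do not support calling the safety analysis p-value-only, the tests useless, or patient safety monitoring deficient.

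**What to change.** In section H, replace the planned testing of adverse effects with wording along these lines: for each adverse effect, the number and percentage of patients in each arm will be given with exact 95% confidence intervals, and the NEPA-minus-placebo risk difference with a 95% Newcombe interval will be the main between-arm result, in all patients who took at least one randomised dose. Because section D.1 offers NEPA to all patients in the open-label extension, the between-arm count should stop before the first open-label dose.

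Either drop the p-values or label them descriptive, with a sentence that a non-significant p-value is not evidence of no excess. Name one interval method in advance, because the methods can disagree: at 7/20 vs 0/10 the Newcombe interval is +2 to +57 points and excludes zero, while Fisher's test gives p = 0.064.

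The cost is a few lines of text and extra table columns, with less emphasis on p-values. Patients, visits and sample size do not change. The interval does not add power; it shows which excesses the data leave open.
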